1. Random coefficient regression model with random intercept and slope will be fitted to the response data. All CombiWISE scores will be included as response variables in the model. In order to model random intercept and slope for pre-and post-treatment separately, factor period (pre vs. post) will be created: pre -treatment (Month -12 to 0) vs. post-treatment (Month 0 (+1 day) to 24). Exact days from the first visit, instead of month will be used as Time in the model. In addition to the random slopes and intercepts, the model will include the fixed effect for treatment group (idebenone or placebo), period (nested within treatment), interaction between Time and period (nested in treatment) and covariates: Baseline (Month 0) CombiWISE score and Baseline age. The interaction between Time and period (nested within treatment) will be used to examine the hypothesis of four slopes are same (slopes for placebo group at pre- and post-treatment, slopes for idebenone group at period pre-and post-treatment). The pairwise comparisons of the four slopes or intercepts,

such as slope (or intercept) at post-treatment for idebenone group vs. that for placebo group, and slope (or intercept) for idebenone group at post-treatment vs. that at pre-treatment period can be constructed and performed using the statement “estimate”. This analysis includes only the observed CombiWISE scores as response variables and as the model can manage incomplete data, no imputation will be done.

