3.2 Adaption of objectives and endpoints

The study was planned to use an adaptive trial design. The trial started with a pre-treatment baseline period of at least 12 months, where magnetic resonance imaging (MRI), clinical and biomarker measurements were collected in all patients for two purposes:

- To obtain longitudinal quantitative MRI, clinical and electrophysiological data in untreated PP-MS patients before randomization. These data will be utilized for the selection of the most sensitive primary outcome measure. This will be done on the first 30 patients and subsequent analysis will be used for selection of the most sensitive primary outcome measure and for adjusting sample size calculation if the primary outcome measure is different than brain atrophy measured by SIENA methodology.
- To obtain patient-specific pre-randomization baseline for all collected outcome measures. This is expected to increase the statistical power of the study ((Murray et al. 2005, Young et al. 2005, Frost et al. 2008). In the study protocol, the following two assumptions were made: 1) CNS tissue destruction develops in a linear manner within a 3-5 year time-frame in the majority of PP-MS patients and 2) the slopes of the linear development of CNS tissue destruction differ among individual patients. Based on these two assumptions, the trial design will allow adjustment for the individualized rates of development of CNS tissue destruction.

The aim of the adaptive trial design was to allow the selection of the most robust (i.e. most sensitive and most accurate) primary outcome measure for the final analysis. Based on the analysis of the pre-treatment phase, the focus of the study shifted from the analysis based on MRI to analysis of clinical endpoints and composite scores. For more details, see section 6 of this SAP.

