13.1.2 Sensitivity analyses

The following sensitivity analyses will be conducted using the ITT population.

- Random coefficient regression model: random coefficient regression model with random intercept and slope will be fitted to the response data. All CombiWISE scores will be included as response variables in the model. In order to model random intercept and slope for pre-and post-treatment separately, factor period (pre vs. post) will be created: pre-treatment (Month -12 to 0) vs. post-treatment (Month 0 (+1 day) to 24). Exact clinic dates for each patient will be used as Time in the model. In addition to the random slopes and intercepts, the model will include the fixed effect for treatment group (idebenone or placebo), period (nested within treatment), interaction between Month and period (nested in treatment) and covariates: Baseline (Month 0) CombiWISE score and Baseline age. The effect of treatment and period (nested within treatment) factors will be used to examine the hypothesis of four intercepts are same (intercepts for placebo group at pre- and post-treatment, intercepts for idebenone group at period pre- and post-treatment). The interaction between Time and period (nested within treatment) will be used to examine the hypothesis of four slopes are same (slopes for placebo group at pre- and post-treatment, slopes for idebenone group at period pre-and post-treatment). This analysis includes only the observed CombiWISE scores as response variables and as the model can manage incomplete data, no imputation will be done.
- Mixed Model for Repeated Measures (MMRM): The change from Baseline to Month 24 in the CombiWISE scores will be compared between the idebenone and placebo groups using MMRM. The observed CombiWISE scores at Months 6, 12, 18 and 24 will be used as response variables in the MMRM. The treatment group, visit and interaction between treatment group and visit will be included as fixed factors. The pre-treatment slope (calculated with linear regression for each patient) and the baseline CombiWISE score will be included as covariates. An unstructured covariance structure will be applied for MMRM. The denominator degrees of freedom will be computed using the Kenward-Roger method. The difference between the groups at Month 24 (and at the other post-baseline visits) and within-group changes within each group will be estimated from the MMRM.

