13.2 Secondary Endpoints

Continuous secondary endpoints (other than the neuroimaging outcomes) will be analyzed using random coefficient regression models similar to the one defined above for the primary outcome variable. In addition, analyses using MMRM will be conducted as well, in order to estimate the treatment differences separately at each visit. The neuroimaging outcomes will be analyzed by calculating AUC values and using ANCOVA models, similar to the primary analysis.

Categorical time-to-event endpoints (EDSS-plus) will be analyzed using Cox Proportional hazards models, with treatment group as a covariate. The patients who do not have an event during the study will be censored at the time of the last assessment of EDSS-plus. The exact number of days from the date of first dose to date of event or censoring will be used as endpoint.

The ITT population will be used for the analysis of the secondary endpoints.

14 Analysis of safety

The safety analyses will be conducted for the following study periods and treatment groups:

- Pre-treatment baseline phase: untreated patients, classified by the treatment group in the double-blind phase and overall
- Double-blind phase: Idebenone treated patients versus placebo treated patients

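### The random coefficient model named first for the continuous clinical secondary endpoints has no stated treatment contrast: its four-slope test also rejects when both arms change pace together, and its arm-specific pre-treatment lines give the slope contrast no gain from the run-in

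*SAP*

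**What the plan says.** SAP 13.1.2, first bullet, fits all CombiWISE scores from Month -12 to Month 24 with random intercepts and slopes by period. The fixed part is "fixed effect for treatment group (idebenone or placebo), period (nested within treatment), interaction between Month and period (nested in treatment"), plus "covariates: Baseline (Month 0) CombiWISE score and Baseline age". Each arm therefore has its own intercept and slope before treatment and again during treatment. The bullet states two hypotheses: that the four intercepts are equal, and, for slopes, "The interaction between Time and period (nested within treatment) will be used to examine the hypothesis of four slopes are same". It names no contrast between the arms.

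SAP 13.2 extends the model: "Continuous secondary endpoints (other than the neuroimaging outcomes) will be analyzed using random coefficient regression models similar to the one defined above". It then adds: "In addition, analyses using MMRM will be conducted as well, in order to estimate the treatment differences separately at each visit". SAP 13.1.2 also fits the random coefficient model to each imputed dataset and asks for the difference between treatment groups, without saying which parameter that is.

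Protocol 11.2 describes the same model and offers pairwise contrasts, "such as slope (or intercept) at post-treatment for idebenone group vs. that for placebo group". The SAP leaves that sentence out, and its introduction says that it supersedes the protocol where the two differ.

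The stated purpose of the run-in is in SAP 3.2: "the trial design will allow adjustment for the individualized rates of development of CNS tissue destruction".

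**The concern.** The efficacy hypothesis in SAP 3.3 and 7 is slower progression on idebenone than on placebo during the two treatment years. That is one comparison. A 3-degree-of-freedom test of four slopes also responds to any change of pace at Month 0 that both arms share, such as a placebo response, a practice effect or non-linear disease. SAP 9 declares significance below 5% without adjustment across secondary endpoints. A reader given the four-slope p-value for EDSS or the timed walk could take it for evidence about the drug.

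The second issue is efficiency. Run-in data precede randomisation, so the expected pre-treatment lines are the same in both arms. Estimating them separately means that a chance imbalance in pre-treatment slope does not inform the treatment-period comparison. That information is what the 12-month run-in was meant to supply.

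**Working it through.** **The plan's own figure.** The only power table (SAP 6.2, Protocol 11.7) is a paired calculation on CombiWISE AUC with mean 51.24, SD 46.2, correlation 0.5 and two-sided 0.05. The SD of a paired difference is 46.2 × √(2 × (1 − 0.5)) = 46.2. The exact paired t-test gives 80.7% for 28 pairs and a difference of 25.62, and 80.2% for 42 pairs and 20.50. Both match the table. It is not a between-arm slope calculation, so only its inputs are used below.

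**Inputs from the documents.** 33 per arm; visits at Months -12, -6, 0, 6, 12, 18 and 24; AUC mean 51.24 and SD 46.2; correlation 0.5.

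**Assumptions.**
- AUC is in point-weeks. A linear rise of b points per year then has a one-year AUC of 26b, so b = 51.24/26 = 1.97, and a 40% effect is 0.788 points per year. The unit cancels from every percentage below.
- The 0.5 is read as the correlation between pre-treatment and scaled treatment-period AUC. The documents do not say that it was estimated that way.
- Each patient's line is continuous at Month 0, true slopes have the same variance σb² in both periods and correlation ρ between periods, and visits have independent noise σe².
- The between-patient intercept SD is 12. SDs of 5 and 20 change no power by more than about 0.1 points.

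**Calibration.** The pre-treatment trapezoid puts weights −0.75, 0.5 and 0.25 on its three visits. Hence 0.25σb² + 0.875σe² = (46.2/52)² = 0.789. Requiring an AUC correlation of 0.5 then fixes the split between slope and noise for each ρ.

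**Calculation.** Generalised least squares with known covariance gives the SD of each estimated contrast. Power is Φ(0.788/SD − 1.96), computed before rounding. The common-line model shares the pre-treatment intercept and slope and leaves the treatment-period intercepts and slopes free by arm.

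| ρ | SD, SAP model | SD, common pre-treatment line | Variance ratio | Power, SAP model | Power, common line |
|---|---|---|---|---|---|
| 0.6 | 0.405 | 0.338 | 0.70 | 50% | 65% |
| 0.8 | 0.361 | 0.281 | 0.61 | 59% | 80% |
| 1.0 | 0.334 | 0.243 | 0.53 | 66% | 90% |

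The SAP column moves with ρ only because holding the AUC correlation at 0.5 changes the noise share. With slope and noise variances fixed, the SAP contrast does not respond to ρ. For a 50% effect with 90% of AUC variance due to slopes, its power is 65% at every ρ from 0.5 to 0.8, while the common-line power rises from 76% to 95%. The Month 0 covariate does not restore the adjustment: for a 50% effect and a slope share of one half, simulation with it gave 81.7%, against 82% analytically without it.

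**Four-slope test with no drug effect.** Let L hold the three slope differences, C be the covariance of the estimates and d = Lβ. The statistic is noncentral chi-square on 3 df with noncentrality d′(LCL′)⁻¹d.

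| ρ | No change of pace | Both arms slow 10% | Both arms slow 20% |
|---|---|---|---|
| 0.6 | 5% | 12% | 36% |
| 0.8 | 5% | 15% | 50% |
| 1.0 | 5% | 18% | 62% |

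In simulations of the SAP model with no drug effect, and with shared slowing of 0, 25% and 50%, the arm contrast of treatment-period slopes rejected in 4.5 to 5.3% of trials.

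**The case against.** Much of the case on the other side stands.

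- **A valid arm contrast exists.** Protocol 11.2 names it, and SAP 16 says the SAP defines the protocol's analyses in more detail, so the omission may not be a conflict. The imputed-data analysis asks for a treatment difference. Nothing in the SAP says the four-slope test will declare efficacy, and it has some bearing on the planned pre-versus-treatment comparison. But no SAP sentence tells the analyst which parameter is the treatment result.
- **The run-in is used elsewhere.** A reader might infer that the secondary analysis discards it. It does not. The MMRM planned for the same endpoints is specified with "The pre-treatment slope (calculated with linear regression for each patient) and the baseline CombiWISE score will be included as covariates", and the primary ANCOVA adjusts for pre-treatment AUC. The loss is confined to the treatment-period slope contrast of this model.
- **Another contrast from the same fit uses the run-in.** The difference between arms in slope change has SDs of 0.391, 0.329 and 0.288 at ρ = 0.6, 0.8 and 1.0, so power of 52%, 67% and 78%. This is better than the treatment-period contrast but below the common-line model, and the SAP does not name it.
- **The largest power gap needs perfectly stable slopes.** A reader might take a gap such as 66% against 90% as the cost. It arises only at ρ = 1.0. SAP 3.1 lists linearity within patients as something the trial will evaluate, and SAP 6.2 says the original sample-size assumptions proved incorrect.
- **Equal pre-treatment lines are not strictly guaranteed in the analysed set.** The ITT population in SAP 8 omits randomised patients with no post-baseline assessment. This is a caveat on the common line, and is small if few patients are omitted.

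**Conclusion.** The point holds and should be fixed, but it does not threaten the primary analysis. The random coefficient model specifies only omnibus tests. The four-slope test rejects in roughly 35 to 60% of trials under a shared 20% slowing, and in 12 to 18% under 10%, with no drug effect. A reader might infer that the model as a whole gives false positives. It does not: the excess belongs to the omnibus test and needs a change of pace common to both arms. If all four slopes are equal it rejects at 5%, and the arm contrast is valid throughout.

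Leaving the pre-treatment lines free costs the treatment-period slope contrast about 15 to 24 points of power for a 40% effect, over slope correlations of 0.6 to 1.0. These figures rest on CombiWISE AUC inputs, 33 per arm, complete data and the assumed reading of the 0.5 correlation. They should not be attached to EDSS, SNRS, 25FW or 9HPT as estimates. For those endpoints the direction carries over as long as a patient's slopes before and during treatment are positively correlated, but the size is unknown.

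**What to change.** In SAP 13.1.2 (first bullet), in the imputed-data analyses and in SAP 13.2:

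1. Name one treatment test for the random coefficient model: treatment-period slope, idebenone minus placebo, with its estimate, 95% confidence interval and p-value.
2. Fit one pre-treatment intercept and slope common to both arms, arm-specific treatment-period lines, and random effects that may correlate between the two periods.
3. Keep the four-slope and four-intercept tests as descriptive, and state that they are not evidence of a treatment effect.

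The cost is a few sentences of SAP text and a small change to the fixed effects. No new data or visits are needed, and the primary ANCOVA and the MMRM stay as they are.

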- 2) To obtain patient-specific pre-randomization baseline for all collected outcome measures, which is expected to increase the statistical power of randomized trials with continuous outcome measures (*Murray, Barer et al. 2005, Young, Lees et al. 2005, Frost, Kenward et al. 2008*). This is because previous longitudinal studies in PP-MS demonstrated that although there is extensive inter-individual variability in the rate of CNS tissue destruction, intra-individually, these rates are relatively stable within 3-5 year follow-up periods (*Ingle, Stevenson et al. 2002, Ingle, Stevenson et al. 2003, Stevenson, Ingle et al. 2004*). In other words: the longitudinal data for the exact MRI, clinical and electrophysiological biomarkers of CNS tissue destruction and clinical disability that we propose to collect in this trial are not available. However, based on published longitudinal studies using analogous, but presumably less sensitive biomarkers of CNS tissue destruction (e.g. ventricular atrophy, cross-sectional cervical spinal cord atrophy collected at 1.5T MRI etc (*Ingle, Stevenson et al. 2003*)) we make two assumptions (Figure 2A): 1. CNS tissue destruction develops in a linear manner within a 3-5 year time-frame in the majority of PP-MS patients and 2. The slopes of the linear development of CNS tissue destruction differ among individual patients. Based on these two assumptions, our trial design will allow adjustment for the individualized rates of development of CNS tissue destruction (Figure 2B), which is expected to increase our power to detect treatment relevant differences between placebo and active therapy groups (*Murray, Barer et al. 2005, Young, Lees et al. 2005, Frost, Kenward et al. 2008*).

The details of analyses of pre-randomization data on the first 30 subjects and the methods for selection of the most sensitive outcome measure are described in detail in Section 11, under Statistical Analyses.

Both active drug and placebo will be supplied by Santhera Pharmaceuticals.

We will use a 2250 mg/day dose (5x150mg tablets three times per day). This dose was well tolerated in Phase I trials in adult patients (*Bodmer, Vankan et al. 2009*) and ensures that each treated patient will receive 10-50mg/kg of idebenone per day, which represents the estimated dose required for CNS efficacy (*Di Prospero, Baker et al. 2007*).

Figure 2
Efficacy measures adjusted for individualized rates of development of CNS tissue destruction in PP-MS

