7. STUDY DESIGN AND METHODS

7.1 Study overview

This is a Phase I/II, double-blind, placebo controlled, baseline versus treatment with 2 parallel study groups (Figure 1) and an adaptive trial design.

Based on current sample size estimates we expect to screen up to 85 PP-MS to yield at least 66 patients that will finish the treatment phase of the study. These patients will be randomized 1:1 to receive either active therapy (idebenone 750mg po tid) or matched placebo. The treatment phase of the trial will be preceded by a 1 year pre-treatment baseline period, which will serve a dual purpose: 1. To collect individualized data on biomarkers of CNS tissue damage and 2. To use these longitudinal data for the selection of the primary outcome measure and for more precise sample size estimates.

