2. Mixed Model for Repeated Measures (MMRM) will be fitted to the response data. The observed CombiWISE scores from all scheduled post-baseline visits (Month 6, 12, 18 and 24) will be used as response variables in the model. The model will include visit, treatment group (idebenone or placebo) and the interaction between visit and treatment group as fixed factors. The Baseline (Month 0) CombiWISE score, baseline age and the rate of decline in the CombiWISE scores during the pre-treatment period will be used as covariates in the model. Both the overall treatment difference at all visits (Months 6, 12, 18 and 24 post-randomization) and the treatment difference separately at each visit will be estimated from the model. The overall treatment difference will be tested based on the fixed factor for the treatment group and the visit-specific treatment differences will be tested with contrasts derived from the fixed factor for treatment group and the interaction term between visit and treatment group. The focus of this analysis will be on the early treatment difference observed at Month 6 post-randomization and the treatment difference at the last study visit (Month 24 post-randomization). An unstructured covariance structure will be applied for the MMRM. The denominator degrees of freedom will be computed using the Kenward-Roger method. The covariate for the rate of decline will be calculated separately for each subject from the CombiWISE scores observed during the pre-treatment period using a random coefficient regression model with random intercept, random slope and time (exact number of days since the first assessment) as an explanatory factor.

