6.2 New sample size calculation

In 2016, a pre-determined analysis of the 58 outcome measures collected in 1 year pre-treatment baseline period on first ≥ 30 IPPOMS patients was performed and published and validated these findings with the 2 validation cohorts consisting of 34 remaining IPPOMS patients and 29 SP-MS patients from RIVITALISE trial (Kosa, Ghazali et al. 2016). This analysis demonstrated that above-stated assumptions or the original sample size calculation were incorrect, that brain atrophy measured by SIENA technology was not more sensitive than clinical outcomes. Instead, based on this pre-defined analysis we selected CombiWISE as primary outcome and brain ventricular atrophy measured by LesionTOADS methodology as secondary outcome.

Up to 85 subjects are planned to be recruited based on current sample size calculation, to account for 20% drop-out and final number of treated subjects 33 per arm (66 total). These recruitment numbers were already achieved and interim analysis of the blinded data of the outcomes showed enhanced, rather than diminished power of new primary outcome (CombiWISE) in comparison to original default primary outcome (Brain atrophy measured by SIENA).

The new power analysis for CombiWISE, EDSS and ventricular volume change has been published for both within-group and between-group designs (Kosa, Ghazali et al. 2016). Using absolute change in the CombiWISE AUC outcome determined from the pre-treatment baseline data in IPPOMS cohort, following power calculation for AUC was derived:

Drug effect	CombiWISE AUC (untreated)	CombiWISE AUC (treated)	CombiWISE AUC (difference)	Actual Power	N Pairs	Distribution	Normal
50%	51.24	25.62	25.62	80.7	28	Method	Exact
45%	51.24	28.18	23.06	80.6	34	Number of Sides	2
40%	51.24	30.75	20.50	80.2	42	Standard Deviation	46.2
35%	51.24	33.31	17.94	80.7	55	Correlation	0.5
30%	51.24	35.87	15.37	80.1	73	Nominal Power	0.8
25%	51.24	38.43	12.81	80.4	105	Null Difference	0
20%	51.24	40.99	10.25	80.2	162	Alpha	0.05

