- *Pre-Treatment Phase Safety Population*

The Pre-Treatment Phase Safety population includes all patients who were enrolled to the study. The patients will be grouped by the treatment actually received in the Double-Blind Phase. The Pre-Treatment Safety population will be used for the safety analysis of the pre-treatment baseline phase.

- *Safety Population*

The Safety population includes all patients who got at least one dose of idebenone or placebo during the double-blind phase. The patients will be grouped by the treatment actually received. The Safety population will be used for the analysis of the safety data from the double-blind phase.

9 General statistical considerations

In general, all data collected in the study database will be summarized by descriptive statistics. Continuous data will be summarized using the mean, standard deviation, standard error of the mean, median, minimum and maximum. Categorical data will be presented in contingency tables with frequencies and percentages.

All hypotheses tests and confidence intervals in this report are two-sided and statistical significance will be declared for p-values below 5%, unless specified otherwise. This study has one pre-defined endpoint. Due to the exploratory nature of the study, no adjustment of the statistical significance level due to multiple secondary endpoints will be done.

10 Demographic and other Baseline characteristics

Demographic and Baseline characteristics will be presented with descriptive statistics for the ITT and Safety populations. These characteristics will be based on the assessment at the study entry (Month -12).

The following endpoints will be summarized:

- Baseline age
- Age at disease onset

-
- Time since disease onset at baseline
 - Body Mass Index
 - History of mononucleosis
 - European ancestry
 - Family history of MS
 - Smoking history

11 Concomitant medication/treatment

All concomitant medications will be listed.

12 Extent of exposure to study medication

The extent of exposure to the study medication will be summarized by tabulating the following:

- The number of patients exposed to study treatment (idebenone or placebo) during the double-blind phase.

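### The sensitivity MMRM gives the pre-treatment slope one coefficient for all visits, so under the plan's own linear-progression assumption the Month 24 contrast gains nothing from the run-in slope

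*SAP*

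**What the plan says.** The MMRM in SAP 13.1.2 models the CombiWISE scores at Months 6, 12, 18 and 24. Its fixed factors are treatment group, visit and their interaction. It then adds: "The pre-treatment slope (calculated with linear regression for each patient) and the baseline CombiWISE score will be included as covariates". The covariance is unstructured, and group differences are estimated at Month 24 and at the other visits. No slope-by-visit term appears.

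Protocol 11.2, sensitivity analysis 2, has the same structure with baseline age added: "the rate of decline in the CombiWISE scores during the pre-treatment period will be used as covariates in the model". There the slope comes from a random coefficient model, and the stated focus is Months 6 and 24.

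The reason for adjusting is in Protocol 4.7, repeated in SAP 3.2. The plan assumes that "CNS tissue destruction develops in a linear manner within a 3-5 year time-frame in the majority of PP-MS patients" and that slopes differ between patients, so adjusting for individual rates should raise power.

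For the continuous secondary endpoints other than neuroimaging, SAP 13.2 uses random coefficient models and adds that "analyses using MMRM will be conducted as well, in order to estimate the treatment differences separately at each visit". It does not list the covariates of those MMRMs.

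**The concern.** If a patient progresses at rate b, the expected score t years after Month 0 is the Month 0 score plus b × t. The run-in slope should therefore carry little weight at Month 6 and much more at Month 24. A covariate entered only as a main effect has one weight for all four visits.

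With an unstructured covariance, that single weight is determined mostly by the early visits, where residual variance is smallest and the slope predicts least. Measurement error at Month 0 lowers it further: the same error enters the pre-treatment slope with a plus sign and every later change from Month 0 with a minus sign.

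What is at stake is precision at Month 24, the contrast that the SAP names for this model.

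**Working it through.** **Inputs from the documents.** SAP 6.2: untreated AUC 51.24, SD 46.2, correlation 0.5, 33 per arm. SAP 9: two-sided 5%. SAP 4.2: visits at Months -12, -6, 0, 6, 12, 18 and 24.

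**Assumptions not in the documents.** The share of pre-treatment AUC variance that is true slope; the correlation of a patient's true slope before and after Month 0 (persistence); reading the table's 0.5 as a pre/post correlation; independent visit errors of equal variance; complete data; and between-patient level variance large enough that the Month 0 score has a coefficient of about 1.

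**1. The plan's own figure.** The SAP 6.2 table is a paired t-test. SD of differences = 46.2 × √(2 × (1 − 0.5)) = 46.2. For the 40% row the noncentrality is 20.50/46.2 × √42 = 2.88, giving 80.2%. All seven rows reproduce. The table concerns pairs; no power is stated for the MMRM.

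**2. Calibration.** Scale the mean rate to 1 per year. Let σb² be the variance of true slopes and σ² the visit error variance. The trapezoidal pre-treatment AUC has mean 0.5 and variance 0.25σb² + 0.875σ². Its SD is 0.5 × 46.2/51.24 = 0.451, so its variance is 0.203. With full persistence, the correlation of pre- with post-treatment AUC is (σb² − 0.4375σ²)/√(0.203 × (4σb² + 3.875σ²)). It equals 0.5 when true slope is 45.8% of 0.203:
- σb² = 0.458 × 0.203/0.25 = 0.372
- σ² = 0.542 × 0.203/0.875 = 0.126

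**3. Coefficient needed at each visit.** With three equally spaced points the fitted slope is the Month 0 score minus the Month -12 score, with variance σb² + 2σ² = 0.624. The coefficient at time t is (tσb² − σ²)/0.624.

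| Month | 6 | 12 | 18 | 24 |
|---|---|---|---|---|
| Coefficient | 0.10 | 0.39 | 0.69 | 0.99 |

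**4. Shared coefficient.** The limiting fit is β = 1′S⁻¹B / 1′S⁻¹1, where B holds the four values above and S is the residual covariance that β itself implies. Iterated to convergence, β = −0.08, below all four values.

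**5. Month 24 residual variance and power.** A 40% slowing is a difference of 0.4 × 1 × 2 = 0.8. The covariance of the slope with the Month 24 change is 2σb² − σ² = 0.619. SE = √(2 × variance/33).

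| Model | Residual variance | SE | 0.8/SE | Power |
|---|---|---|---|---|
| No slope covariate | 4σb² + 2σ² = 1.741 | 0.325 | 2.46 | 68% |
| As written | 1.741 + 2 × 0.08 × 0.619 + 0.08² × 0.624 = 1.84 | 0.334 | 2.39 | 65% |
| Slope × visit | 1.741 − 0.619²/0.624 = 1.128 | 0.261 | 3.06 | 85% |

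The variance ratio, as written against slope × visit, is 1.64. In this case the model as written does slightly worse than one with no slope covariate.

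**6. Range.** Set slope × visit to 80% power at Month 24 and vary the assumptions:

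| Meaning given to the 0.5 | Persistence | True-slope share | Variance ratio | Power as written |
|---|---|---|---|---|
| AUC with AUC | 1.0 | 45.8% | 1.64 | 59% |
| AUC with AUC | 0.8 | 58.8% | 1.54 | 62% |
| Slope with Month 24 change | 1.0 | 38.2% | 1.43 | 65% |
| Slope with Month 24 change | 0.55 | 86.5% | 1.35 | 67% |

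The losses are 21, 18, 15 and 13 points. If true slope is 25% or less of the AUC variance, the loss is at most 7 points (80% to 73% at a 25% share with full persistence); there the shared coefficient is clearly negative, −0.16 to −0.37. Over shares of 10% to 90% and persistence of 0.4 to 1.0, the loss runs from under 1 point to about 65.

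**7. Simulation check.** Two scenarios, 600 trials of 66 patients each, complete data, t reference with 62 df in place of Kenward-Roger. Power with slope × visit against as written was 82.8% against 61.5% (share 44%, persistence 1.0) and 76.8% against 57.2% (share 60%, persistence 0.8). The shared coefficient averaged −0.08 in both.

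**The case against.** The strongest reply has four parts.

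- **This is not the primary analysis.** The primary test in SAP 13.1.1 is an ANCOVA on one scaled AUC per patient, adjusted for pre-treatment AUC, Month 0 score and age. It has no visit dimension, so the run-in year is used where the main conclusion is drawn. The random coefficient model also handles pre- and post-treatment slopes directly. This stands.
- **Growth with time is conditional.** The linearity statement concerns CNS tissue destruction, not CombiWISE, and testing it is a secondary goal (Protocol 5.2). Protocol 11.4 says that the original sample-size assumptions, which include stable individual atrophy rates, were incorrect. The blinded AUC check in Protocol 11.2 (coefficient 3.96) fits roughly linear progression during treatment, but does not show that a patient's three-point run-in slope persists afterwards. This stands as a condition on the size. It does not rescue the single coefficient, because the covariate is there on the strength of that same assumption.
- **The size is not fixed.** No slope reliability or persistence for CombiWISE is given, the 0.5 belongs to a table of pairs, and the figures above assume complete data although recruitment is planned "to account for 20% drop-out". This stands, so only a range can be given.
- **The secondary endpoints are not computed.** SAP 13.2 does not list the covariates of those MMRMs, and noisier component slopes would mean smaller losses. The figures also follow the SAP's per-patient slope, not the protocol's random-coefficient version. Both limits stand.

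**Conclusion.** The single slope coefficient is at odds with the assumption that justifies the covariate. Under that assumption the Month 24 MMRM contrast gains nothing from the run-in slope. With a pre/post correlation of 0.5, complete data, 33 per arm and 80% power for the slope × visit model, the loss is about 13 to 21 points. It is 7 points or less if true slope is 25% or less of the pre-treatment AUC variance.

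Two stronger readings are tempting. A reader might infer one fixed loss of around 20 points; the documents lack the slope reliability and persistence needed to fix it. A reader might also infer that the treatment estimate is biased or that the trial's main result is weakened. Treatment is randomised, so the contrast remains unbiased, and the primary ANCOVA does not contain this term. The practical risk is a noisier sensitivity analysis that seems to disagree with the primary one. The point is a cheap improvement.

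**What to change.** Add pre-treatment slope × visit to the MMRM in SAP 13.1.2. List the covariates of the MMRMs in SAP 13.2, and include the same term wherever the slope is a covariate. The SAP supersedes the protocol where they differ, so editing the SAP is enough, though aligning Protocol 11.2 would be tidy.

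The cost is three extra fixed-effect parameters (four visit-specific coefficients in place of one) and no new data. Month 24 power was at least as high with the term in every scenario examined. Baseline score × visit is optional: the shared baseline coefficient is already about 1, and the term shows no added gain here.

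Protocol 7.6 reports that the analysis is complete, so a refit for this trial would have to be labelled post hoc.
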